4.3 RANDOMIZATION PLAN

The randomization procedure will be based on creating a block for every 4 subjects with 2 subjects of each treatment randomly positioned in the block. Withdrawal is covered in section 5.5. This should provide balance among the two arms for rates of mucositis by disease. If imbalance exists after randomization, covariates will be used for adjustment of the results.

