2	02/24/2016	
Added updated DSMC language as requested by the MCW DSMC on 1/22/15:
 
This study will be reviewed by the Medical College of Wisconsin Cancer Center Data and Safety Monitoring Committee (MCWCC DSMC). A summary of the MCWCC DSMC activities are as follows:
 
 • Review the clinical trial for data integrity and safety. • Review all unexpected grade 3, and all grade 4, and 5 adverse events, as well as any others requiring expedited reporting as defined in this protocol. (Grades 4 & 5 events must be reported to the DSMC within 5 calendar days of study staff’s knowledge.) • Review all DSM reports. • Submit a summary of any recommendations related to study conduct. • Terminate the study if deemed unsafe for patients. 
A copy of the MCWCC Data and Safety Monitoring Plan and membership roster will be maintained in the study research file and updated as membership changes. The committee will review reports from the study PI twice annually (or more frequently if needed) and provide recommendations on trial continuation, suspension or termination as necessary. Any available DSMC letters will be submitted to the IRB of record as required.
	
YES –
 
Footers/Headers only– updated to protocol v2 Dated 2/24/2016
 
 • Consent Spanish Short Form • HIPAA Adult • HIPAA Adult Spanish • HIPAA Child • HIPAA Child Spanish

SYNOPSIS

Study Title: A Randomized Controlled Trial Investigating Topical Caphosol for Prevention of Oral Mucositis in Children, Adolescents and Young Adults (AYA) Receiving Chemotherapy

Randomized Controlled Trial

[figure not shown]
Number of Patients: A total of 96 patients will enroll to this study with 48 patients in the Caphosol group and 48 patients in the control group.

Study Objectives

- **Primary Objectives**
 - To determine if topically administered Caphosol at the initiation of chemotherapy prevents the development of oral mucositis (Grade ≥ 2) in children, adolescents and young adults.
 - To determine the tolerability of four times daily Caphosol therapy.

- **Secondary Objectives**
 - To determine if topically administered Caphosol reduces the severity of oral mucositis, as measured by incidence of severe mucositis (CTCAE v4.0 Grades 3 or 4), age-appropriate pain scores (FACES and Likert), use of narcotic pain medicine, number of hospital days and duration of total parenteral nutrition (TPN).

Treatment Plan Schema

Caphosol Administration:

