3.0 SELECTION OF PATIENTS

Study patients will be recruited from the MACC Fund Center and the oncology inpatient service. Study entry is open to patients regardless of gender or ethnic background. While there will be every effort to seek out and include females and minority patients, the patient population is expected to be no different than that of other oncology studies at the Medical College of Wisconsin.

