4.0 REGISTRATION PROCEDURES

Registration will occur after eligibility is confirmed and the patient/parent has signed the subject consent, but before any treatment has been administered.

The eligibility checklist will be completed at the time of study enrollment.

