4.1 Registration

Upon completion of the screening evaluation, eligibility confirmation and obtaining written consent, the patient will be registered in the study file by the Department of Pediatrics Division of Hematology/Oncology/BMT MACC Fund Center Clinical Trials Office (CTO). When the OnCore™ Clinical Trials Management System (CTMS) is fully functioning for this study, the MACC Fund Center CTO will use this program for patient registration.

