5.0 TREATMENT PLAN

This study is a randomized, controlled trial evaluating the use of topical Caphosol therapy to prevent oral mucositis (Grade ≥ 2) in children, adolescents and young adults undergoing chemotherapy. At the time of enrollment, patients will be randomized to either the control arm or the Caphosol arm. The treatment period will extend from the start of chemotherapy and continue for 7 days after completion of chemotherapy AND until the ANC is > 500 after nadir (count recovery) or until the symptoms of oral mucositis resolve; whichever occurs last.

Treatment

Caphosol Arm: Subjects randomized to the **Caphosol Arm** will use Caphosol 4 times per day as follows:

- Each dose consists of two 15 mL syringes, to be mixed at time of administration. Caphosol must be used within 15 minutes of mixing.
 - Subjects may increase the use to 6 times per day if they have symptoms of mucositis.
- Using one of the syringes, rinse and gargle (if patient is able) for one minute and then spit. Repeat using the remaining syringe.
 - For younger patients (less than or equal to 6 years of age), volume may be reduced to two syringes containing 5-10 mL each.
 - For patients unable to successfully rinse and spit, caregivers may paint their mouth (using medical sponge swabs) with the solution two times. Prior to swabbing the patient's mouth, squirt one of the syringes into a cup and using the medical sponge, soak up the solution and use the swab to coat the inside of the patient's mouth. Repeat using the second syringe.
- Patients are to avoid other oral medications, other mouth cares and food or drink for 15 minutes after using Caphosol.

- Patients will also use Biotene (5-10 mL) to swish and spit after the 15 minutes has passed. Biotene is part of our standard of care to prevent oral infections in oncology patients.

Control Arm: Subjects randomized to the **Control Arm** will use Biotene only 4 times per day as follows:

- Use 5 to 10 mL of Biotene to swish and spit
 - For patients unable to successfully rinse and spit, caregivers may paint their mouth (using medical sponge swabs) with the solution two times. Prior to swabbing the patient's mouth, pour Biotene into a cup and using the medical sponge, soak up the solution and use the swab to coat the inside of the patient's mouth. Repeat with a second swab.

The following will be observed:

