10.0 STATISTICAL CONSIDERATIONS

10.1 Statistic Endpoints

The study will not stratify based on diagnosis. The effectiveness of the study will be based on comparing incidence and severity of oral mucositis. Safety and tolerance will be based on the differential incidence of severe adverse events. A continuous sequential boundary will be used to terminate the study if the difference in adverse events occurs at a rate of 10% or greater at the interim analysis performed at the end of study month 3. A continuous sequential boundary will also be constructed for a differential rate of 5%.

An interim analysis will be conducted half way through using the O'Brien-Fleming rule for early stopping because of success.

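### The fixed, printed block size of 4 in Section 4.3 lets a recruiter who tracks every earlier assignment know up to a third of the next ones with certainty

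*Combined protocol and SAP*

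**What the plan says.** Section 4.3 (Randomization Plan) describes "creating a block for every 4 subjects with 2 subjects of each treatment randomly positioned in the block". It gives no other block size. Section 10.1 adds that "The study will not stratify based on diagnosis", and no other stratification factor is named, so the natural reading is one running sequence. The synopsis sets the size: "A total of 96 patients will enroll to this study with 48 patients in the Caphosol group and 48 patients in the control group".

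The arms can be told apart. Under Section 5.0 the Caphosol arm uses Caphosol and Biotene, while controls "will use Biotene only 4 times per day as follows". No placebo rinse and no masking are described.

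On setting and order, Section 3.0 says "Study patients will be recruited from the MACC Fund Center and the oncology inpatient service". Section 4.0 says "Registration will occur after eligibility is confirmed and the patient/parent has signed the subject consent", and Section 4.1 gives registration to the Clinical Trials Office, through OnCore once that system is working. Section 5.0 places randomization at enrollment. No section says who generates or holds the list, or how the next assignment is withheld until a patient is committed. If the arms turn out unbalanced, Section 4.3 plans covariate adjustment but names no covariates.

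**The concern.** With a known block of 4, once two patients in a block have received the same arm, the next two assignments are fixed. After any three, the fourth is fixed. The prediction rests on past assignments, which are not masked here, so it can be made before the next patient is approached. Consent before registration does not prevent it, and neither would concealing the list alone.

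Section 1.0 states that incidence and severity depend on age, diagnosis, regimen, oral hygiene and genetic factors. A recruiter can see several of these. If lower-risk patients were approached when Caphosol was known to be next, or higher-risk patients when control was next, the result would look like prevention. Adjustment after the fact reaches only what was measured and put in the model. Blocking without stratification balances arm totals; it does not protect the balance by disease that Section 4.3 expects.

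**Working it through.** **Inputs.** Block of 4, two per arm (Section 4.3). Total 96, 48 per arm (synopsis). One sequence (Section 10.1 excludes stratification by diagnosis; no other factor is named). The documents give no figure for predictability. Their totals agree with the block design: 96/4 = 24 blocks, and 24 × 2 = 48 per arm.

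**Assignments known with certainty.** A 2:2 block has 6 equally likely orders.
- Positions 1 and 2: never known.
- Position 3: known if the first two match, in 2 of 6 orders, so probability 1/3.
- Position 4: always known.

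Expected number per block = 0 + 0 + 1/3 + 1 = 4/3. The general formula for a block of 2m is 2m/(m+1), which gives 4/3 at m = 2. As a share this is 1/(m+1) = 33.3%. Over 24 blocks: 24 × 4/3 = 32 of 96, with SD √(24 × 1/3 × 2/3) = 2.3.

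**Best-guess rate.** Guessing the arm that is behind is right with probability 1/2, 2/3, 2/3 and 1 at the four positions. The mean is 2.833/4 = 70.8%, or 68 of 96, against 50% under simple randomization.

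**Alternatives.** The rows for fixed blocks are enumerated. Those for mixed blocks are simulated (400 trials of 96) for an observer who sees every earlier assignment and knows the set of possible sizes.

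| Scheme | Known with certainty | Best guess right |
|---|---|---|
| Fixed 4 | 33.3% | 70.8% |
| Fixed 6 | 25% | 68.3% |
| Fixed 8 | 20% | 66.6% |
| Random 2, 4, 6 | about 4% | about 70% |
| Random 4, 6, 8 | about 2% | about 68% |
| Simple randomization | 0% | 50% |

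Hiding the sizes hardly changes the last column, because guessing the arm that is behind needs no knowledge of block size. For 4, 6 and 8: (4 × 0.708 + 6 × 0.683 + 8 × 0.666)/18 = 0.68.

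**What steering could do (illustration; risks assumed, not from the documents).** Suppose half the patients have 25% risk and half 50%, and Caphosol has no effect. If a fraction c of the known third is steered, the expected spurious difference is c × (1/3) × 25 points. Simulation of 96 patients with a two-sided 5% test gave:

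| Fraction of known slots steered | Spurious difference | Type I error |
|---|---|---|
| 0 | 0 points | 5% |
| 1/4 | 2 points | 5% |
| 1/2 | 4 points | 7% |
| All | 8 points | 13% |

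**The case against.** Fixed blocks of 4 are a legitimate choice, and Section 10.3 calls the study a pilot for a larger one. The strongest objections concern access to information and room to act.

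- A reader might infer that recruiting staff see every past assignment and that one team screens, approaches and schedules patients. The documents do not say so. Patients are identified in clinic or on the ward (Section 2.0), the Clinical Trials Office registers them (Section 4.1), and Investigational Pharmacy dispenses Caphosol (Section 7.1.6). Section 4.1 concerns registration; silence about who holds the list does not show that the recruiting office controls it. This stands, and it makes one third an upper limit.
- A reader might also infer wide, known risk gaps between the listed agents. No agent-specific rate is given, and the synopsis and Appendix 1 describe all of them as carrying a high incidence. Section 1.0 supports variation in risk, not its size.
- Room to delay an approach may be small. Caphosol starts on Day 1, and Section 3.1 enrols at the start of oncology therapy. The synopsis, however, admits patients at any point in therapy. The two passages must be reconciled, and the room for timing depends on the answer.
- Varying the block sizes hardly lowers the best-guess rate. This stands too, and it limits what the fix can claim.

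The safeguards already planned (consent and eligibility before registration, and covariate adjustment) do not stop a prediction made from earlier visible assignments.

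**Conclusion.** The point holds as an avoidable exposure to selection bias. Up to one third of assignments, 32 of 96 in expectation, could be known in advance. This assumes an observer who has the complete ordered record, knows the block boundaries and works with a single sequence. That the trial is unmasked is inferred from the arms and the absence of any blinding text. The documents do not support saying that a third of assignments will in practice be known, or that anyone would steer; they show only that it is possible. The size of any bias cannot be derived from the documents, and the 8-point case is the extreme of an assumed scenario. The arithmetic is certain; the staffing and visibility conditions are not. The change is worth making because it is cheap.

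**What to change.** In Section 4.3:
- Replace the fixed block of 4 with randomly varied block sizes, leaving out blocks of 2 (for example 4, 6 and 8).
- State the sizes only in a document kept from recruiting staff.
- Have the study statistician generate and hold the list.
- Release each assignment, through OnCore or the registrar, only after consent and eligibility are locked. Section 4.0 already puts both before registration; what is missing is the explicit link to release of the assignment.

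This cuts certain assignments from 33% to about 2% (about 4% with 2, 4 and 6). The best-guess rate moves only from 71% to about 68%, so the revised text should not claim that allocation becomes unpredictable.

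The cost is a new list and a few changed sentences. If enrollment ends inside a block of 8, the arms could differ by up to 4 patients, at worst 50 against 46. The equivalent equal-arm size is then 2 × 50 × 46/96 = 47.9 per arm instead of 48, a negligible loss of power.

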1.0 BACKGROUND

Mucositis in Children, Adolescents and Young Adults Undergoing Chemotherapy

Oral mucositis, a common and debilitating complication of cancer therapy, is an inflammatory injury to the epithelial and sub-epithelial cells of the oral mucosa. Oral mucositis is thought to develop according to a five-stage model: 1) initiation; 2) up-regulation with generation of messengers; 3) signaling and amplification 4) ulceration with inflammation; and 5) healing, and typically develops 7-14 days into a chemotherapy course (1).

The incidence and severity of oral mucositis depends on many factors including the age and diagnosis of the patient, the specific treatment regimen, underlying oral hygiene and genetic factors (2-4). The incidence of oral mucositis in patients receiving chemotherapy ranges from around 40% of patients receiving myelosuppressive chemotherapy for solid tumors to 70-90% of patients receiving myeloablative therapy prior to stem cell transplant (1, 5, 6). A commonly used grading scale for mucositis is the Common Terminology Criteria for Adverse Events (CTCAE version 4.0) grading scale, where grading is based on both subjective and objective assessments on a 5 point scale (Grade 1 to Grade 5).

Adverse Event	1	2	3	4	5
Mucositis Oral Definition: A disorder characterized by inflammation of the oral mucosal.	Asymptomatic or mild symptoms; intervention not indicated	Moderate pain; not interfering with oral intake; modified diet indicated	Severe pain; interfering with oral intake	Life-threatening consequences; urgent intervention indicated	Death

From the Common Terminology Criteria for Adverse Events (CTCAE) Version 4.0 Published: May 28, 2009 (v4.03: June 14, 2010) U.S. DEPARTMENT OF HEALTH AND HUMAN SERVICES National Institutes of Health National Cancer Institute, p. 19

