10.2 Statistical Analysis

Comparisons of binary outcomes such as prevention of oral mucositis will use logistic analysis or Fisher's exact test if the numbers are small. Comparisons of the severity of oral mucositis (an ordinal scale) will use the Wilcoxon rank sum test since the data is on a 5 point Likert scale, although there are really only two levels of values. Similarly for the secondary outcome an ordinal pain scale can be treated as an ordinal scale. Length of stay and duration of TPN will use a t-test plus a log transform, if necessary to reduce the skewness of the data. Otherwise the Wilcoxon test will be used.

Although there may be loss to follow-up, we don't expect it because continued

chemotherapy depends on the clearing of the mucositis.

The primary analysis for mucositis will be based on a binary scale (Grade 1 versus Grade ≥ 2 mucositis) because the mucositis essentially has only two clinically pieces to the scale. It also represents common clinical practice.

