10.3 Sample Size Justification

For an alpha of 0.05 and a power of 80%, 48 subjects per group allow detection of a 30% difference in the incidence of oral mucositis (range of oral mucositis is 25% to 50%). Efficacy assessment will occur at study completion.

Twenty subjects per group can detect a 0.6 unit difference in the toxicity scale. This is based on an effect size of 0.90 and a SD of 0.66 units. This is a medium sized clinical difference using Cohen's criteria. This study will serve as a pilot for a larger study. For toxicity, which can only be estimated in the treatment group, 48 subjects in the Caphosol group will allow estimation of a 95% confidence interval of the toxicity of about $\pm 15\%$. Assessment of toxicity will occur once the study enrolls 20 patients to each arm to obtain a preliminary estimate (95% CI) for toxicity and again at study completion (to obtain a more precise estimate). While the study is stopped if it passes the sequential boundary, to obtain an estimate of the toxicity and its 95% Confidence interval (95% CI) both an interim analysis and an analysis at the end of the study will be used to estimate the 95% CI – most precisely at the end of the study.

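### Section 4.3 credits unstratified blocks of 4 with balance by disease and adjusts only if imbalance is seen; a fixed primary model that always adjusts for one regimen group and one age group would be better

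*Combined protocol and SAP*

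**What the plan says.** Section 4.3 describes the randomization as "creating a block for every 4 subjects with 2 subjects of each treatment randomly positioned in the block", with no stratification factor. It continues: "This should provide balance among the two arms for rates of mucositis by disease". The next sentence is the adjustment rule: "If imbalance exists after randomization, covariates will be used for adjustment of the results".

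Section 10.1 confirms the absence of strata: "The study will not stratify based on diagnosis". Section 1.0 says that the incidence and severity of oral mucositis "depends on many factors including the age and diagnosis of the patient, the specific treatment regimen", along with oral hygiene and genetic factors.

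On the test itself, section 10.2 says: "Comparisons of binary outcomes such as prevention of oral mucositis will use logistic analysis", or alternatively Fisher's "exact test if the numbers are small". The primary endpoint is binary (Grade 1 versus Grade 2 or higher). Neither 4.3 nor 10.2 names a covariate, a size of imbalance that counts, an adjusted model, or what counts as small numbers.

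**The concern.** Blocking without strata forces equal numbers in the two arms after every fourth patient. It does nothing to the mix of diagnoses, regimens or ages within the arms, so the expectation of balance by disease is unsupported.

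The rule that follows is the practical weakness. Whether the primary model has covariates, and which ones, is decided after the baseline data are in and possibly after outcomes are known. Two analysts following 4.3 faithfully could report different primary p-values. Section 10.2 adds a second open choice: the unstratified Fisher's exact test takes no covariates, so 4.3 can call for adjustment while 10.2 calls for a test that cannot adjust.

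At stake are a modest loss of control over type I error if the choice is exploited, and a modest loss of precision, because adjustment for prognostic factors helps whether or not those factors happen to be imbalanced.

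**Working it through.** **Inputs from the plan.** 96 patients, 48 per arm (synopsis); blocks of 4, two per arm (4.3); alpha 0.05, power 80%, 30-point difference (10.3). The pair of rates behind the 30 points and the sidedness of alpha are not given.

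**Assumed, because the documents are silent.** Group sizes of one third or one half of patients; odds ratios (OR) for the two groups as shown below; two-sided tests.

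**1. The plan's own figure.** Take 55% versus 25%, one pair that is 30 points apart.
- Uncorrected: n = [1.96·√(2·0.40·0.60) + 0.8416·√(0.55·0.45 + 0.25·0.75)]² / 0.30² = (1.358 + 0.555)² / 0.09 = 40.7, so 41.
- Continuity-corrected: (40.66/4)·[1 + √(1 + 4/(40.66·0.30))]² = 47.1, so 48 per group.

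This reproduces the plan's 48. Because other pairs are possible (50% versus 20% gives 39, or 45 corrected), 55% versus 25% is a working assumption and not the plan's statement.

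**2. Balance.** Suppose 32 of 96 patients belong to a disease group and X of them fall in the Caphosol arm. The gap between arms is |2X − 32|/48. A gap of 10 points or more needs |2X − 32| ≥ 4.8, that is X ≤ 13 or X ≥ 19. With a plain 48:48 split, X is hypergeometric (96, 32, 48), and each tail is 0.1395, total 0.279. Simulated blocks of 4 also give 0.279. If the group size itself varies around one third, the figure is 0.328. For a group with 50% prevalence, simulation gives 35.6% with blocks and 36.1% without.

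**3. How often the condition would be met.** At a 10-point threshold, two independent factors each at 50% prevalence give 1 − (1 − 0.356)² = 0.585. One factor at one third (0.328) and one at one half (0.356) give 1 − 0.672·0.644 = 0.567. Adjustment is triggered in over half of trials. For a single factor at 50%, the chance is about 36%, 12.5% and 5% at thresholds of 10, 15 and 20 points, so the unstated threshold matters.

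**4. Type I error (simulated, nominal 5%).**

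| Analysis | Type I error |
|---|---|
| Unadjusted | 4.6-5.5% |
| Always adjusted for two factors | 4.9-5.3% |
| Fixed 10-point trigger, no picking | 4.3-5.0% |
| Best of the allowed models, 15-point trigger | 5.0-5.2% |
| Best of the allowed models, 10-point trigger | 5.5-5.7% (two covariates), 5.8-5.9% (three) |
| Best of the allowed models, 5-point trigger | 5.9-6.5% |

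**5. Power at 55% versus 25%** (6,000 trials each, Monte Carlo error about 0.5 point).

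| Assumed OR, regimen / age | Unadjusted | 10-point trigger | Always adjusted | Gain from always adjusting |
|---|---|---|---|---|
| 1 / 1 | 86.2% | 85.6% | 85.7% | −0.5 |
| 2 / 1.5 | 85.4% | 85.3% | 86.4% | +1.0 |
| 3 / 2 | 85.4% | 86.3% | 88.0% | +2.6 |
| 5 / 2 | 86.5% | 87.9% | 90.4% | +3.9 |

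With ORs of 3 and 2 the trigger captures 0.9 of the 2.6 points available. At 50% versus 25%, where power is lower, the same ORs give 72.4% unadjusted and 76.2% always adjusted.

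**6. Can the data carry two more terms?** Expected events at 55% versus 25% are 48·0.55 + 48·0.25 = 38.4, or about 13 for each of the three slopes.

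**The case against.** The strongest reply is that this is under-specification and not an error-inflating rule. An unadjusted test is valid under randomization, and chance imbalance is not bias. A fixed 10-point trigger keeps type I error at or below nominal. The excess appears only if someone chooses the most favourable permitted model, which 4.3 does not describe, and at a 15-point trigger even that stays at 5.0-5.2%. All of this stands.

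It is also fair that the power gain rests on prognostic strengths the documents do not give, that it vanishes if the groups do not predict mucositis, and that section 10.3 calls the study a pilot for a larger one. Always adjusting is a preference between valid methods; what matters most is that one is fixed in advance.

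Two points of wording also stand. Section 4.3 places the balance sentence next to the conditional rule but does not make one the reason for the other. It speaks of the results in general, so applying the rule to the primary analysis is the natural reading and not an explicit statement.

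What does not survive is the balance claim, or a defence of leaving covariates, threshold and model open when section 1.0 already names the likely drivers.

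**Conclusion.** The point holds as a modest, inexpensive improvement. Unstratified blocks of 4 do not balance disease groups: the chance of a gap of 10 points or more is 28% for 32 of 96 patients. The conditional rule leaves the primary model open in over half of trials at a 10-point threshold. Exploiting that choice would lift type I error to roughly 5.5-6.5% at triggers of 10 or 5 points. Always adjusting is worth about 1 to 3 points of power for moderately prognostic groups, more for stronger ones, and between zero and a 0.5-point loss for groups that are not prognostic. Group sizes, odds ratios and the pair of event rates are assumptions.

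A reader might infer three stronger things that the documents do not support:
- That the trial is biased or its unadjusted test invalid. Imbalance here is chance, and the test allows for it.
- That the small fixed block shows a failure of allocation concealment. Sections 4.0, 4.1 and 5.0 put registration after consent and eligibility and randomize at enrollment. Nothing shows that enrolling staff can follow the sequence.
- That the plan cannot cope with few events. Fisher's exact test is available for that, and has 80.8% power at 55% versus 25%. Its shortcomings here are the missing trigger and the inability to adjust.

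**What to change.** In 4.3, delete the sentence on balance by disease and the condition on observed imbalance. In 4.3 and 10.2, state that the primary logistic model always contains treatment arm, one regimen group and one age group, whatever balance is observed.

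Define both groups before outcomes by arm are seen. Set the regimen group from the qualifying agents at enrollment, with a rule for patients receiving several listed agents, because treatment and evaluation continue over later courses (5.4, 5.5). Fix the age cut in the same place.

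Replace Fisher's test as the primary fallback with a method that keeps the same groups, used when the fit fails or when an arm or covariate level has no events or only events. Penalised logistic regression is one option: in simulation, type I error was 4.3-5.2%, and power at 50% versus 20% was 89.4%. An exact test stratified by the two groups is another: type I error 3.7%, power 86.1%, against 82.5% for unadjusted Fisher. Report the unadjusted Fisher test and the risk difference as sensitivity results.

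Cost: a few sentences, the work of defining two groups, two more model terms, and an odds ratio that is conditional on those groups, which is why the unadjusted risk difference should stand beside it. No extra patients or data are needed: the eligibility checklist (Appendix 1) records the qualifying agents and checks age, and demographics are entered at consent (9.1).
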